Cover page:

Official Title of the study:

Effectiveness of recorded hypnosis, virtual reality or their combination in patients undergoing a bone marrow examination at the hematology unit

Date: July 5th, 2023

Background:

A bone marrow (BM) examination is an invasive procedure performed at the hematology unit under sedation and local anesthesia. Before the procedure, most patients report anxiety, both related to the procedure itself and results' expectation. Moreover, BM examination itself may cause other symptoms including pain with an increase in the use of analgesics. Various non-pharmacological techniques, including hypnosis (H) and virtual reality (VR) exist today and are used as complementary tools in the treatment of anxiety and pain, including around procedures. Hypnosis is defined as "a state of altered consciousness that includes focused attention and reduced peripheral awareness, characterized by an improved ability to respond to suggestiveness." This technique is considered safe and allows the patient to be focused on his inner self, by including cognitive and behavioral components that allow the mind to influence the body's sensations and perceptions. Many studies show the positive effect of hypnosis on symptoms such as pain or anxiety. VR is another technique that gives the user the illusion that he is in a different realistic environment than he really is. Studies have shown that VR can isolate the patient from the external environment and distract attention from a painful stimulus. As for surgery or invasive procedures, a few studies have examined the effect of H, VR or their combination (VRH) with variable results.

Therefore, the purpose of the present study is to examine the effect of a hypnotic script (H), virtual reality (VR) or their combination (VRH) on common symptoms surrounding bone marrow examination.

Methods:

Study setting: We are planning a 4-arms open-label randomized-controlled trial that will take place at the Hematology Unit of Bnai Zion Medical Center in Haifa, Israel.

Ethics review: The study protocol was reviewed and approved by the Institutional Review Board in accordance with the Helsinki Declaration (0053-23-BNZ).

Study population: Eligible participants will be recruited from the hematological unit at Bnai-Zion Medical Center in Haifa, Israel. Inclusion criteria: (1) Aged 18 or older, (2) Candidate for a BM examination at the hematology unit, (3) Able to answer questionnaires in Hebrew, Arabic or Russian, and (4) Signed an informed consent form. Exclusion criteria include (1) Hearing impairment and (2) Visual impairment.

Randomization: Patients meeting the inclusion criteria who agree to participate in the study will be randomly assigned by blocked randomization in a 1:1:1:1 ratio to one of the following 4 groups: control group (C), hypnosis only group (H), virtual reality only group (VR) and combined hypnosis group with virtual reality (VRH).

Blinding: Due to the different types of interventions, the study cannot be blinded.

Interventions: All patients will undergo the BM procedure under local anesthesia with or without sedation according to local guidelines. Additionally, patients randomized to intervention groups (H, VR and VRH) will receive the different interventions after arriving to the clinic and when waiting for the procedure. These include:

Hypnosis (H): Patients will be given earphones to hear a hypnotic script that was recorded by [name], a psychologist specializing in hypnosis after observing about ten BM examinations at the hematology institute. The length of the recording is about 7 minutes.

Virtual reality (VR): Patients will be connected to a VR device that will transmit to the patient's choice a 3D screen and soothing noise for about 7 minutes.

Combined hypnosis and virtual reality (VRH): Patients will hear the same 7-minute hypnotic script by earphones and simultaneously be connected to the VR device that will show the 3D screen without soothing noise.

Outcomes:

Primary outcome: The primary outcome will be the effect of the intervention on different symptoms experienced by patients undergoing BM procedure. This outcome will be evaluated by the Measure Yourself Concerns and Wellbeing (MYCAW) questionnaire that examines two main problems that are bothering the patient at the time, including a rating on a Likert scale from 0 to 6. Patients will fill out the questionnaire upon arrival to the clinic (before intervention), 10 minutes after intervention and before starting the procedure (or about 20 minutes after the first questionnaire filling for control group), and when waking up from the procedure. MYCAW questionnaire is appropriate due to its validity, translation into relevant languages, combination of both quantitative and qualitative data, and appropriateness to complementary medicine studies.

Secondary outcomes: The effect of the interventions on absorption, dissociation, immersion and time perception will be evaluated by a short validated questionnaire that will be given to the patients 10 minutes after intervention before the BM examination. The effect of the interventions on sedation and analgesics use during and after the BM examination will be evaluated by specifically recording the type and dose of sedatives and analgesics given to the patient during and after the procedure. Finally, the effect of the interventions on physiological indicators will be evaluated by measuring vital signs (blood pressure, pulse, respiratory rate) before and during the BM examination.

Safety and adverse events: The interventions are safe and no significant side effects are expected. Patients will be directly asked for the potential appearance of adverse events during or immediately after the intervention. All adverse events will be recorded, monitored and addressed accordingly. The intervention may be stopped if significant side effects are of concern.

Criteria for discontinuation: Participants may be discontinued from the study if they voluntarily withdraw informed consent, for safety reasons or due to significant non-compliance with the study protocol as judged by the Principal Investigator. Reasons for discontinuation will be recorded and patients withdrawn from the study will be included in the intention-to-treat analysis.

Quality control: A Data Safety Monitoring Board constituted of five experts will control the safety, and quality of the intervention as well as data collection on a yearly basis. Dropout, withdrawal, treatment adherence and uncollected data will be recorded until completion of the study.

Sample size calculation: Since no previous study has evaluated similar data, we estimated that a minimum of 100 patients (25 patients in each group) was required to achieve a clinical effect of the interventions.

Statistical methods: Data analysis will be performed using IBM SPSS Statistics software.

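### Planned sedation is not recorded before allocation or used in the randomisation; one yes/no item would add precision and guard against chance imbalance

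*Protocol*

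**What the plan says.** Sedation appears in three roles in the protocol.

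- **Background care.** Interventions: "All patients will undergo the BM procedure under local anesthesia with or without sedation according to local guidelines". The guidelines are not reproduced, and the protocol does not say who decides on sedation or when.
- **Outcome.** Secondary outcomes: the effect on sedation and analgesia is to be assessed by "recording the type and dose of sedatives and analgesics given to the patient during and after the procedure".
- **Condition under which later measures are taken.** Secondary outcomes include "measuring vital signs (blood pressure, pulse, respiratory rate) before and during the BM examination". The MYCAW, the primary instrument, is completed a third time "and when waking up from the procedure". Its second completion is "10 minutes after intervention and before starting the procedure".

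The Randomization section describes one blocked 1:1:1:1 scheme and names no stratification factor. No section asks for the intended sedation to be noted before the arm is known. The sample size section gives 25 patients per group.

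The sections also differ on how usual sedation is. The Background calls the examination an "invasive procedure performed at the hematology unit under sedation and local anesthesia", and the third MYCAW presumes a patient who wakes up. The Interventions section allows procedures without sedation.

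**The concern.** If some patients are due for sedation under the guideline and others are not, planned sedation is likely to be a strong predictor of sedative use. It may also predict blood pressure, pulse and respiratory rate during the examination, and how the patient feels on waking. With 25 patients per arm, an unstratified scheme can leave the arms visibly uneven on such a factor. An uneven split could resemble an effect on sedative use or hide one. Without a record made before allocation, it could be neither seen nor adjusted for. A later analysis plan cannot repair this, because it cannot use an item that was never collected.

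**Working it through.** **Inputs.** From the protocol: 25 patients per arm, four arms (4 × 25 = 100), blocked randomisation with no named stratum. The share of patients due for sedation is not given, so 30%, 50%, 80% and 90% are assumed. The protocol has no figure of its own on this point to reproduce.

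**1. Chance imbalance between two arms.** Let X and Y be the numbers with planned sedation in two arms, each Binomial(25, p). A gap of 20 percentage points is 0.20 × 25 = 5 patients. The SD of the difference in proportions is √[2p(1−p)/25]; the probability is the exact binomial sum of P(|X−Y| ≥ 5).

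| p (assumed) | SD of difference | P(gap ≥ 20 points) |
|---|---|---|
| 0.30 | 0.130 | 0.164 |
| 0.50 | 0.141 | 0.203 |
| 0.80 | 0.113 | 0.110 |
| 0.90 | 0.085 | 0.034 |

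The chance that at least one of the three active arms differs from control by this much is about 36%, 44% and 26% at p = 0.30, 0.50 and 0.80.

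**2. Is the unadjusted comparison biased?** One active arm was compared with control in 100,000 simulated trials. Assumed probabilities of actual sedation in control: 0.90 if planned, 0.20 if not. With the intervention: 0.65 and 0.10. At p = 0.50 the true difference is (0.5 × 0.65 + 0.5 × 0.10) − (0.5 × 0.90 + 0.5 × 0.20) = 0.375 − 0.550 = −0.175.

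| p | True | Mean unadjusted estimate |
|---|---|---|
| 0.30 | −0.145 | −0.146 |
| 0.50 | −0.175 | −0.175 |
| 0.70 | −0.205 | −0.206 |

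There is no bias. With no true effect, the unadjusted z test rejected in 5.2% to 6.4% of trials, which is its usual small-sample behaviour.

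**3. What does the recorded plan buy?** At p = 0.50, stratifying the analysis by planned sedation leaves the mean estimate at −0.175 and lowers its SD from 0.139 to 0.108. The ratio of information is (0.139/0.108)² ≈ 1.65. The gain is precision.

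**4. Dose as the outcome.** Take mean dose 1 and SD s in the sedated, and zero dose otherwise. The sedated/not-sedated split then explains p(1−p)/[p(1−p) + p·s²] of the variance. At p = 0.50: 0.25/(0.25 + 0.5 × 0.09) = 0.85 for s = 0.3, and 0.25/(0.25 + 0.5 × 0.25) = 0.67 for s = 0.5. At p = 0.80 the shares are 0.69 and 0.44. These describe planned sedation only as far as sedation given follows the plan.

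**5. Why not adjust for sedation received?** An illustrative simulation let anxiety raise both the chance of sedation and the MYCAW score, let the intervention lower the chance of sedation, and gave it no effect on MYCAW. The randomised comparison showed a difference of 0.00. Within the actually sedated and the actually unsedated, spurious differences of 0.14 and 0.13 points appeared.

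**The case against.** A reader might infer that the effect on sedation cannot be separated from the case mix. The documents do not support that. Case mix is fixed before allocation, the trial is randomised, and the arm difference in sedatives given estimates the total effect without knowing any patient's plan; step 2 shows this.

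It is also fair to say that the imbalance figures are ordinary binomial variation, already allowed for in a valid standard error, and that any unstratified factor of the same prevalence would give them. That stands: they describe lost precision and the risk of an awkward single trial, not an inflated error rate. The risk also shrinks where sedation is nearly universal, which the Background and the waking time point suggest.

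A reader might further infer that staff who know the arm choose the sedation and so create a difference. The trial is unblinded, but the protocol does not say who decides or when, so this remains a possibility and is not shown.

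Finally, much of how sedation is handled in analysis belongs in a statistical analysis plan that is not shown, and leaving out stratification is not an error. What survives is narrower: collecting the item before allocation is a matter of conduct, and has to be settled before patients are randomised.

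**Conclusion.** This is a cheap improvement, not a flaw that invalidates the sedation outcome. The protocol gives sedation three roles and provides for no pre-allocation record of the plan. The cost is precision and exposure to chance imbalance: a gap of at least 20 points between two given arms has a chance of roughly 11% to 20% if 30% to 80% of patients are due for sedation, and about 3% at 90%. Under the assumed rates in step 3, using the plan in the analysis is worth about 1.65 times the information on whether sedation is given. All of this rests on assumed sedation rates.

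The outcomes concerned are sedative use, vital signs during the examination and the waking MYCAW. For the last two, the randomised comparison still gives the total effect, including any part that runs through sedation. The second MYCAW is outside the concern.

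Separately, and without any assumption, the Background, Interventions and Primary outcome sections do not fit together on whether sedation is routine, and the third MYCAW has no defined time in a patient who was not sedated.

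**What to change.** - Record for each patient, before the allocation is revealed, whether sedation is planned under the local guideline (yes/no).
- Stratify the blocked randomisation by this item, or at least adjust for it when analysing sedative use, vital signs during the examination and the waking MYCAW.
- Keep all randomised patients in the main comparison. Treat a dose comparison within the planned-sedation group as supportive only; at 50% planned sedation it would rest on about 25 × 0.5 = 12.5 patients per arm.
- Do not condition on sedation actually received.
- Reconcile the Background, Interventions and Primary outcome sections on whether sedation is routine, and state when the third MYCAW is completed in patients who are not sedated.

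**Cost.** The sedation plan must be stated before allocation, which may be earlier than at present, and stratifying means two block lists instead of one. No extra patients or visits are needed. No change to who is sedated is proposed.

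### The only solicited adverse-event question is timed by the intervention, with no matching time for controls and none after the procedure

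*Protocol*

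**What the plan says.** Under Safety and adverse events, the protocol starts from a premise, "The interventions are safe and no significant side effects are expected", and then sets out how harms are to be found: "Patients will be directly asked for the potential appearance of adverse events during or immediately after the intervention". The next sentence adds "All adverse events will be recorded, monitored and addressed accordingly", with no limit by arm or time. No other active enquiry about adverse events is described.

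Under Interventions, "patients randomized to intervention groups (H, VR and VRH) will receive the different interventions after arriving to the clinic and when waiting for the procedure". The control arm has no session. The procedure itself is common to all arms: "All patients will undergo the BM procedure under local anesthesia with or without sedation according to local guidelines".

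Under Primary outcome, MYCAW is completed three times: on arrival, 10 minutes after the intervention and before the procedure, and after the procedure. For the second and third of these the text reads "or about 20 minutes after the first questionnaire filling for control group), and when waking up from the procedure". Controls therefore have a defined time for the second questionnaire although they have no session.

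**The concern.** How an adverse event comes to light affects how many are counted. A direct question brings out minor symptoms that patients would not otherwise mention. If three arms have a defined occasion for that question and the fourth has none, the counts are not collected on the same footing, and randomisation does not repair this.

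That matters here for three reasons. Most patients are described as anxious beforehand, and every arm undergoes an invasive procedure under local anesthesia, with sedation in some cases, so background symptoms are plausible in controls too. The trial is open-label, so staff know which patients had a session. And the monitoring board that is to oversee safety each year would see data gathered in this way.

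What is at stake is the interpretability of the adverse-event data, not the primary outcome. The point belongs to the protocol rather than the SAP: an analysis cannot recover answers to a question that was not asked.

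**Working it through.** The protocol gives no adverse-event rate and plans no safety calculation, so there is no figure to reproduce. The check is mainly a comparison of the texts.

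**Step 1: who has a defined occasion for each enquiry**

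| Occasion | MYCAW, H/VR/VRH | MYCAW, control | Solicited AE question, H/VR/VRH | Solicited AE question, control |
|---|---|---|---|---|
| Arrival | yes | yes | none stated | none stated |
| Around the session | none | none | yes | no session, no substitute time |
| Before the procedure | 10 min after the session | about 20 min after the first | none stated beyond the session | none stated |
| After the procedure | yes | yes | none stated | none stated |

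**Step 2: does another reading of the sentence close the gap?** The time phrase can be attached in two ways.
- If it fixes when the question is put, controls have no such moment, and the question comes before the procedure.
- If it fixes when the events must have appeared, the moment of asking is open. The window of interest is still defined by the session, so controls have no window, and events that first appear later lie outside the question.

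Reading the word intervention as the bone marrow procedure does not fit either. The protocol keeps the two terms apart, and the same paragraph goes on to speak of stopping the intervention.

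**Step 3: the two gaps act differently.** The missing control time separates the arms directly. The missing post-procedure question applies to all four arms. By itself it lowers capture everywhere, and it biases a comparison only if spontaneous reporting or observation differs by arm, which is possible without blinding.

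**Step 4: illustration of size.** Let the true rate be p in every arm, with capture probability s1 in the active arms and s0 in controls.

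Apparent difference = p × (s1 − s0), while the true difference is 0.

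The values of p, s1 and s0 are assumptions; none is in the document.

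| p | s1 | s0 | Apparent difference |
|---|---|---|---|
| 10% | 1 | 0.5 | 5 points |
| 10% | 1 | 0 | 10 points |
| 20% | 1 | 0.5 | 10 points |
| 30% | 1 | 0.5 | 15 points |
| 30% | 1 | 0 | 30 points |
| any | s | s | 0 |

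In patients, at the planned minimum of 25 per arm and with p = 20%, s1 = 1 and s0 = 0.5: 75 × 0.20 = 15 active patients recorded (20%), against 25 × 0.20 × 0.5 = 2.5 controls (10%).

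**Step 5: do the existing contacts serve?** A session of about 7 minutes plus the 10-minute wait gives about 17 minutes, before set-up time, if the first questionnaire directly precedes the session. The control time is about 20 minutes. The second MYCAW therefore falls at a similar elapsed time in all arms.

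**The case against.** The strongest reply is that the protocol says patients, without naming arms, and promises to record every adverse event. A reader might infer from the timing that controls are never asked, that later events in the active arms are missed, and that safety has no comparator. The text supports none of these.
- Controls are not excluded from the question; they simply have no stated time for it.
- Later events are unsolicited, which is not the same as missed, because they fall under the promise to record all events.
- A randomised control arm exists, so a comparison would be weakened rather than absent.

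It is also fair that no comparative safety claim is planned. Adverse events are neither a primary nor a secondary outcome, and the statement that the interventions are safe is a premise. For a session of about 7 minutes, asking around the exposure is a reasonable choice in itself.

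There is partial cover as well. MYCAW asks every arm about two bothersome problems at each contact, sedatives and analgesics are recorded during and after the procedure, and vital signs are taken before and during it. None of these is an adverse-event enquiry, but a prominent symptom in a control could come to light through them.

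Finally, the upper end of the illustration needs full capture in the active arms and none in controls, which the document does not say.

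All of this limits the point. What remains is that recording whatever becomes known does not equalise how it becomes known, and that a site following the text has no instruction on when to ask a control patient, or any patient after the procedure.

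**Conclusion.** The point holds in a limited form. The only solicited enquiry is defined relative to the intervention, with no equivalent for controls and none after the procedure. Elsewhere, events depend on spontaneous report or observation, so any account of adverse events by arm is open to ascertainment bias.

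Its size cannot be derived from the document. The 5 to 30 points in the illustration rest wholly on assumed rates and capture, and the bias would be zero if sites in practice asked all arms alike.

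This is a minor but inexpensive improvement. It does not touch the primary outcome and does not show that any intervention is unsafe.

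**What to change.** Keep the enquiry during and just after the session. In addition, put one identically worded adverse-event question to all four arms at two existing contacts: the second MYCAW (about 20 minutes after the first for controls) and the third MYCAW (on waking from the procedure). State in the safety section that controls are included. How the answers are tabulated can be left to the SAP.

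The cost is one extra question at two contacts that already take place, and a few more minor events on record. No visit is added and no treatment changes.

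Because the enquiry around the session remains specific to the active arms, a like-for-like comparison should rest on the answers to the common question.

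### Patients can be taken out of this unblinded trial for non-compliance on the investigator's judgement, and nothing requires their remaining outcomes to be collected for the promised intention-to-treat analysis

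*Protocol*

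**What the plan says.** The paragraph Criteria for discontinuation opens: "Participants may be discontinued from the study if they voluntarily withdraw informed consent". It then adds two further grounds: safety, and removal "due to significant non-compliance with the study protocol as judged by the Principal Investigator". What is discontinued is participation in the study. The level at which non-compliance becomes significant is not defined. Reasons are to be recorded, and "patients withdrawn from the study will be included in the intention-to-treat analysis".

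On masking, the Blinding paragraph states: "Due to the different types of interventions, the study cannot be blinded".

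Elsewhere the protocol keeps apart what the discontinuation paragraph runs together. The safety paragraph deals with the intervention alone: "The intervention may be stopped if significant side effects are of concern". Quality control lists adherence separately from leaving the trial: "Dropout, withdrawal, treatment adherence and uncollected data will be recorded until completion of the study".

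Under Primary outcome, MYCAW is completed on arrival, again 10 minutes after the intervention, and on waking from the procedure. For controls the second rating is due "about 20 minutes after the first questionnaire filling for control group". No section says whether these ratings, or the secondary outcomes, are still collected once a patient has been discontinued.

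**The concern.** Intention-to-treat needs two things: each patient analysed in the assigned arm, and outcomes observed whatever part of the intervention was received. The protocol secures the first and leaves the second open. A patient who is in the analysis set but has no rating after baseline contributes only a baseline value or whatever an imputation method supplies.

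The risk can differ by arm. Controls can breach the protocol too, for example by missing the timed second questionnaire. Only H, VR and VRH, however, have a session to comply with, so removals are likely to fall mainly, though not solely, on those arms. The person deciding knows the allocation. Patients who refuse or break off a recording or headset session may also differ in anxiety or other symptoms from those who complete it.

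The amount lost depends on timing. A patient removed during the session may lack the second and third MYCAW ratings and the questionnaire on absorption, dissociation, immersion and time perception. Drug use and vital signs recorded by staff may still exist. A later removal loses less.

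**Working it through.** The protocol gives no removal rate, no SD and no named test, so there is no figure of its own to reproduce on this point. The calculation below shows scale only.

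**Inputs**
- From the protocol (Sample size calculation): 25 patients per arm.
- Assumed: *k* = 1 to 4 of 25 patients in one active arm are removed with no later ratings.
- Assumed: removed patients differ from those retained by *g* = 0.5 to 1 SD.
- Assumed: only observed ratings are analysed, with a two-sided 5% t-test of one active arm against control, and there is no true effect.

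**Shift in the active-arm mean** = (*k*/25) × *g*
- 1/25 × 0.5 = 0.02 SD
- 1/25 × 1 = 0.04 SD
- 2/25 × 1 = 0.08 SD
- 4/25 × 0.5 = 0.08 SD
- 4/25 × 1 = 0.16 SD

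**If one control of 25 is also lost and differs by the same amount**, the net bias is ((*k* − 1)/25) × *g*
- *k* = 1: 0
- *k* = 4, *g* = 0.5: 3/25 × 0.5 = 0.06 SD
- *k* = 4, *g* = 1: 3/25 × 1 = 0.12 SD

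**Against sampling error.** The standard error of a 25-versus-25 difference is √(2/25) = 0.283 SD. Then 0.02/0.283 = 7% and 0.16/0.283 = 57%.

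**False-positive rate.** This uses the noncentral t distribution with noncentrality = bias / √(1/n₁ + 1/n₂) and n₁ + n₂ − 2 degrees of freedom.

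| Patients analysed (active v control) | Bias (SD) | Rejection rate at nominal 5% |
|---|---|---|
| 24 v 25 | 0.02 | 5.05% |
| 23 v 25 | 0.08 | 5.8% |
| 21 v 25 | 0.08 | 5.8% |
| 21 v 25 | 0.16 | 8.3% |
| 21 v 24 (one control also lost) | 0.12 | 6.8% |

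If the ratings are collected after removal, the bias from this source is zero.

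**The case against.** The strongest reply is that the protocol is silent rather than wrong. It nowhere says that collection stops, it keeps withdrawn patients in the intention-to-treat analysis, and an unseen SAP may say how missing ratings are handled. The clause is permissive and limited to significant non-compliance. Reasons, adherence and uncollected data are all recorded, and a five-member board reviews data collection yearly, so selective removal would be visible. The intervention lasts about 7 minutes within a single procedure visit, so removals may be few. A patient who refuses the questionnaires, which can happen in any arm, would yield no MYCAW rating under the proposed wording either. Finally, once collection continues, deleting non-compliance as an exit ground adds little.

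Much of this limits the size of the problem, and that part stands: nothing in the document suggests frequent removals, the heavier burden on active arms is inferred, and refused questionnaires cannot be recovered by wording.

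It does not remove the point. The protocol does state a rule: non-compliance is a ground for leaving the study. Recording and oversight make losses visible but do not prevent them. Whether a questionnaire is handed to a patient is trial conduct, which the protocol governs; an SAP can only choose how to treat a rating that was missed. Leaving the exit ground in place would also keep a rule that invites staff to stop collecting.

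**Conclusion.** The concern holds. An investigator who knows the allocation may remove patients from the study on an undefined standard, and intention-to-treat inclusion is promised without securing the data it needs. The primary outcome is the most exposed, because its two later ratings must be completed by the patient around one procedure.

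The direction and size of any bias are unknown. Under the assumed removals and differences it is 0.02 to 0.16 SD (0.02 to 0.08 SD for one or two removals), with false-positive rates of 5.1% to 8.3%. The upper end needs 4 of 25 (16%) removed from one arm, a full 1 SD difference, no control lost and no later ratings. The effect is small unless removals are frequent. The change should still be made, because the missing ratings cannot be recovered and prevention costs very little. Confidence is medium, since the protocol does not say what happens to data collection after removal.

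**What to change.** Amend Criteria for discontinuation so that not completing the intervention is distinct from leaving the study, and delete non-compliance as a ground for leaving the study. State that the remaining MYCAW ratings, the absorption questionnaire, the sedative and analgesic record and the vital signs are collected for every randomised patient, whatever part of the intervention was received, unless the patient withdraws consent to data collection. Analyse each patient in the assigned arm. The provisions on safety and on stopping the intervention stay as they are.

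The cost is about one sentence of collection wording, the deletion of one ground, and whatever ethics notification the amendment needs. Extra data collection is minimal because all outcomes are gathered around a single procedure.

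### Does the unsupported claim that 100 patients are needed for a clinical effect call for a change to the sample size section?

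*Protocol*

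**What the plan says.** The Protocol, under Sample size calculation, opens with its only reason, "Since no previous study has evaluated similar data", and then gives the number and the claim attached to it: "we estimated that a minimum of 100 patients (25 patients in each group) was required to achieve a clinical effect of the interventions". Nothing else appears under that heading.

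Other parts of the Protocol bear on how to read it:

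- Background states the aim: "the purpose of the present study is to examine the effect of a hypnotic script (H), virtual reality (VR) or their combination (VRH").
- Randomization says patients will be "randomly assigned by blocked randomization in a 1:1:1:1 ratio to one of the following 4 groups". Blinding says the trial cannot be blinded.
- Primary outcome uses MYCAW, with two problems each rated 0 to 6, and includes a baseline: "Patients will fill out the questionnaire upon arrival to the clinic (before intervention").
- Criteria for discontinuation keeps withdrawn patients in the intention-to-treat analysis.
- Quality control provides yearly oversight: "A Data Safety Monitoring Board constituted of five experts will control the safety", together with the quality of the intervention and the data collection. Dropout is to be recorded, but no allowance for it is given.

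**The concern.** Four things look wrong at first sight.

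1. **The claim.** No number of patients is needed for an intervention to work. A number is needed to detect or estimate a stated difference, and none is stated.
2. **The reason.** Lack of earlier data explains why no calculation was made, but 25 does not follow from it. A difference and a range of SDs could have been assumed on a 0 to 6 scale, or feasibility could have been named.
3. **The word minimum.** It sets a floor, with no ceiling and no rule for ending recruitment. In an unblinded trial, recruitment that runs on after outcomes have been seen could inflate the type I error.
4. **The unit.** The text does not say whether 25 counts randomised or evaluable patients.

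The stake would be interpretation. A reader told that the necessary size was reached might take a non-significant arm as evidence that the intervention does nothing. A moderate effect could easily be missed at 25 per arm.

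**Working it through.** **Inputs from the Protocol:** four arms, 1:1:1:1, 25 per arm, outcome rated 0 to 6, baseline measured. **Not in the Protocol, so assumed:** two-sided 5%, 80% power, one active arm against control, 25 analysed per arm, no multiplicity adjustment, SD of 1 to 2 points.

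**Step 1. The plan's own figure.** 4 × 25 = 100, so the total agrees with the arm size. The 25 itself cannot be reproduced, because no input to it is given.

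**Step 2. What 25 per arm detects.** By the normal approximation,

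d = (z₀.₉₇₅ + z₀.₈₀) × √(2/n) = (1.960 + 0.842) × √(2/25) = 2.802 × 0.283 = 0.79 SD.

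The noncentral t with 48 df gives 0.81 SD. Using the normal-approximation value of 0.79, this is about 0.8, 1.2 or 1.6 points at an SD of 1, 1.5 or 2. The 95% confidence interval half-width is t₀.₉₇₅,₄₈ × √(2/25) = 2.011 × 0.283 = 0.57 SD.

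**Step 3. Baseline adjustment.** With residual SD √(1 − r²) and 47 df, the detectable difference is 0.77, 0.70 or 0.58 SD at r = 0.3, 0.5 or 0.7. The correlation is assumed.

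**Step 4. The size needed depends on the assumed effect.** n per arm = 2 × (2.802)² / d²:

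| Assumed d | n per arm | Total | Power with 25 per arm (normal approximation) |
|---|---|---|---|
| 0.5 | 63 | 252 | 42% |
| 0.6 | 44 | 176 | 56% |
| 0.8 | 25 | 100 | 81% |
| 1.0 | 16 | 64 | 94% |

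With Bonferroni for three comparisons with control, the detectable difference at 25 per arm rises to 0.94 SD (noncentral t). So 100 is generous, adequate or short according to an effect size that the document does not give. The agreement at 0.8 SD cannot be taken as the sponsor's basis.

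**Step 5. Several arms together.** If each intervention truly had a 0.8 SD effect, all three unadjusted comparisons would be significant in about 60% of simulated trials, and at least one in about 95%. The Protocol sets neither criterion. Its aim names the interventions as alternatives, so the lower figure shows no shortfall.

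**Step 6. Floor and unit.** A minimum number required is the usual way to state a target. The board's remit covers safety, quality of the intervention and data collection. No efficacy look, and no decision to extend recruitment on results, is described anywhere. Blocked equal allocation keeps the arms close to balanced at whatever total is reached. Keeping withdrawn patients in the intention-to-treat analysis, together with the allocation statement, makes randomised patients the natural reading of 25 per group, though the text does not settle it.

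**The case for a change.** The best case for a change is that this is not a matter left to an unseen SAP. The Protocol chose to give a sample size rationale, and the one it gives does not support the number. A reader cannot tell whether 25 came from an effect size, from feasibility or from habit. Loose English for detect does not rescue the sentence, since detection needs a stated difference. With no blinding and no stated end to recruitment, a firm total would also close off any suspicion about when the trial stopped. The repair would be one line, with no extra patient or visit.

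Part of this stands. The sentence justifies nothing, and it should not be cited later as evidence that the trial was adequately sized. A true effect of 0.5 SD would be missed in about 59% of trials without adjustment (noncentral t, power 41%), or in 32% with adjustment at r = 0.7.

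The rest does not carry. The 0.5 SD effect is a reviewer's choice. The misreading of a null arm needs a reader to draw an inference that the Protocol never makes, and the confidence interval will show the imprecision whatever this sentence says. The risk from an open total needs outcome-driven extension, which the document does not describe. The one-line repair would only fill in a reason that the sponsor alone knows. A precision statement built on assumed correlations could be mistaken for the sponsor's design basis.

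**Conclusion.** The observation is right and the consequence is small. The number 100 has no stated basis, and the phrase attached to it is poor wording, most plausibly meant as the size needed to detect an effect. The documents do not show that 100 is too few, that the missing ceiling causes bias, or that all three arms must succeed.

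The only size that can be put on the point is conditional. At 25 analysed per arm, two-sided 5% and 80% power, one comparison with control detects about 0.81 SD unadjusted, or 0.77 to 0.58 SD with baseline adjustment at an assumed correlation of 0.3 to 0.7. Nothing in the Protocol says whether that is good enough.

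Stating the reason for 25 would improve the reporting but would leave the number, arms, assessments and analysis as they are. A trial run as written would yield the same data and the same estimates, so this is a gap in explanation and no change to the plan follows. Results should be read from the estimates and their intervals, not from the claim that the necessary size was met.
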